For post-treatment immunogenicity assessment, subjects who complete the Week 48 visit will be asked to return to clinic to have blood samples collected approximately every 3 months for up to [REDACTED] AEs and concomitant medications will also be recorded during the immunogenicity follow-up period. Additional testing may be requested in the event of safety-related concerns.

The sponsor may elect to terminate participation in the immunogenicity follow-up period based on emerging data. Subjects who terminate IP early will not return for immunogenicity follow-up, unless asked to return for additional testing(s), at the Medical Monitor's discretion.

Main Study

After signing informed consent, subjects will undergo screening assessments to determine eligibility over a period of 12 weeks. In line with the FDA guidance, in instances where COVID-19 pandemic restrictions or logistical scheduling challenges may be of concern, the screening period may be extended beyond 12 weeks with Sponsor approval(FDA, August 2021).

On Day 1 (baseline), eligible subjects will be randomized 16:8:6:24:15 to Placebo QW, Placebo Q2W, pegozafermin 15 mg QW, 30 mg QW and 44 mg Q2W, respectively. The randomization will be stratified by Type 2 diabetes mellitus (T2DM) status (yes vs no) and fibrosis stage (F2 vs F3). For the purposes of stratification, subjects will be considered to be T2DM status positive if any of the following criteria are met: current medical history of T2DM, current use of anti-glycemic medication(s) for T2DM, or screening laboratory values of $\geq 6.5\%$ for HbA1c or ≥ 126 mg/dL for fasting plasma glucose. IP will be administered over 24 weeks (includes 24 administrations in QW dose regimen and 12 administrations in Q2W dose regimen). In the Main study, subjects, investigators and site staff, and Sponsor will be blinded to IP (placebo or pegozafermin); however, the dose regimen (QW or Q2W) will be known to all parties involved in the study. Subjects will undergo a second liver biopsy at the Week 24 visit (window of -7 days to +14 days). Liver biopsies will be read centrally by liver pathologists who are blinded to the treatment group assignment (refer to Section [6.4.3](#) for details).

Extension Study

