MRI-PDFF	X			X	X				X	X			At Screening, MRI-PDFF should ideally be done before liver biopsy. At Screening, a historical MRI-PDFF assessment performed within the last 3 months prior to screening may be acceptable if the images are available and evaluable by the central imaging vendor. On treatment, MRI-PDFF should ideally be done within ± 7 days of the target visit date. If out of the window, MRI-PDFF should be performed as close to the target visit date.
cT1	X			X	X				X	X			Iron-corrected T1 mapping. Applicable only at sites capable of conducting cT1 imaging. At Screening, a historical cT1 assessment performed within the last 3 months prior to screening may be acceptable if the images are available and evaluable by the central imaging vendor.
Liver/Spleen volume and pancreatic fat	X			X	X				X	X			To be done at the same time as MRI-PDFF. At Screening, a historical liver/spleen volume and pancreatic fat assessment performed within the last 3 months prior to

Assessments	Screening Period ¹	Treatment Period										FU Period		Notes:	
		Main Study					Extension Study								
Study Day		1 ²													
Study Weeks	-12 to 0		4 ³	8 ⁴	12 ³	16 ⁴	24 ³	26 ⁵	30 ⁴	38 ³	48 ³	ET ^{3,6}	51 ^{7/} EOS		
Visit window (days)			±2	±7	±7	±7	+7	+7	±7	±14	+14		±14		
														screening may be acceptable if the images are available and evaluable by the central imaging vendor.	
Bone Mineral Density (BMD) by Dual X Ray Absorptiometry (DXA) ^r		X				X				X	X			r. DXA should be done within -14/+7 days of the target visit date. If out of the window, DXA should be performed as close to the target day as possible.	
Plasma for bone biomarkers analysis		B		X		X				X	X			Includes CTX, P1NP, and osteocalcin; refer to Appendix 2 (Section 10.2).	
Endogenous FGF21 ^s		B												s. Baseline samples of endogenous FGF21 will be obtained in all subjects; additional samples will be obtained at the immunogenicity follow-up visits (See Table 2). Endogenous FGF21 samples (baseline and follow-up visit) will be analyzed only in subjects with neutralizing ADAs.	
Immunogenicity		B	X	X	X		X		X	X ^t	X			t. See Table 2 for immunogenicity follow-up.	
Pharmacogenomic (DNA) blood sampling		X												Optional.	
Blood sample for exploratory biomarkers		X				X			X	X					
Adverse event monitoring ^u	X	X	<=====X=====>						X	X				u. The sites may take non-personally identifying photographs of potential injection site reactions (optional).	
Concomitant medications	X	X	<=====X=====>						X	X					

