3.2. Dosage And Administration

On Day 1 (baseline) of Main Study, eligible patients will be randomized 16:8:6:24:15 to Placebo QW, Placebo Q2W, pegozafermin 15 mg QW, 30 mg QW and 44 mg Q2W, respectively. IP will be administered over 24 weeks (includes 24 administrations in QW dose regimen and 12 administrations in Q2W dose regimen). Patients will undergo a second liver biopsy at the Week 24 visit (window of -7 days to +14 days). Liver biopsies will be read centrally by liver pathologists who are blinded to the treatment group assignment.

Patients completing the Main Study will continue for an additional 24 weeks in the Extension Study. The Extension Study will commence at Main Study Week 24 visit. Patients randomized to placebo QW in the Main Study will be re-randomized 1:1 to pegozafermin 30 mg QW (n=21) or placebo QW (n=21) and receive the re-randomized treatment beginning at the Week 26 visit (which may be an in-clinic or a remote home visit by healthcare professional who will administer the IP.). All other patients will continue to receive the same treatment regimen in the Extension Study that they received during the Main Study. IP will be administered over 24 additional weeks (includes 24 administrations in QW dose regimen and 12 administrations in Q2W dose

regimen), for approximately 48 weeks of treatment over the entirety of the study (Main and Extension). Specifically-identified Sponsor personnel will not be blinded; however, subjects, investigators and site staff will remain blinded to IP (placebo or pegozafermin). Dose regimen (QW or Q2W) will be known to all parties in the Extension Study.

Table 1: Number of Subjects and Intervention Groups

Treatment Group	Dose	Frequency	Route of Administration	Number of subjects
Placebo	-	QW	SC injection	42*
Placebo	-	Q2W	SC injection	22
Pegozafermin	15 mg	QW	SC injection	16
Pegozafermin	30 mg	QW	SC injection	64
Pegozafermin	44 mg	Q2W	SC injection	40

* At Week 24, subjects randomized to placebo QW in the Main Study will be re-randomized 1:1 to pegozafermin 30 mg QW (n=21) or placebo QW (n=21).

*Abbreviations: QW, weekly; Q2W, every 2 weeks; SC, subcutaneous.

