5.2. Actual Treatment Group

Primary Analysis for Main Study

If a subject receives only placebo doses, then their actual treatment group will be placebo group. If a placebo subject incorrectly received at least one pegozafermin active dose, then they will be counted as the pegozafermin active treatment group in the highest dose group received for safety analysis. If a pegozafermin subject receives at least one dose of pegozafermin active treatment, then the most frequent dose received will be considered as the actual treatment group.

Final Analysis

In the final analysis, the actual treatment arm will be assigned following the same rule as in the primary analysis for Main Study for subjects who were not re-randomized in the Extension study.

The actual treatment group will be assigned as pegozafermin in the highest dose level if subject switched from Placebo to pegozafermin in the Extension Study. However, subjects who switched the treatment in the Extension Study will be summarized under ‘Placebo (main) and

Pegozafermin 30 mg QW (Extension)" group as a separate column in the final safety summaries and efficacy analysis.

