7. STATISTICAL METHODS OF ANALYSES

7.1. General Considerations

The primary analysis will include data up to the min of (28 days after the last dose date before the completion of all Week 24 assessments, the date all Week 24 assessments completed, Main Study cut-off date).

At final analysis, safety summaries including extent of exposure will report data from both Main Study and Extension Study, based on safety analysis set.

Continuous variables will be summarized by number of patients, mean, standard deviation (SD)/ standard error (SE), median, minimum, and maximum values. Minimum and maximum will be presented to the same number of decimal places as reported/collected. One additional decimal place will be presented for mean and median. Two additional decimal places will be presented for SD/ SE up to a max of three decimal places.

Categorical variables will be summarized by number and percentage of patients. Percentage will be presented to one decimal place. The number of missing values will be presented as a separate category with no percentage, but only if 1 or more patients are missing data for the summary. Otherwise, all categories will be presented (even if no patients are counted in the category). Counts of zero in any category will be presented without percentage.

For analysis purpose, placebo QW and placebo Q2W will be pooled except for exposure summaries and pre-specified supportive analyses.

All statistical tests will be 2-sided and tested at a statistically significant level of 0.05 without adjustment for multiplicity. Confidence intervals will be 2-sided 95%, unless stated otherwise. Two-sided p-values will be presented with four decimal places and values less than 0.0001 will be presented as <.0001.

Both reported units (CN) and standard units (SI) will be presented in listings. Only CN units will be used for tables and figures, unless otherwise specified. Insulin will be presented with conventional unit of μ IU/mL.

All applicable analyses for the primary analysis of the Main Study will be presented as:

<Description>	Placebo Pooled	Pegozafermin 15 mg QW	Pegozafermin 30 mg QW	Pegozafermin 44 mg Q2W
---------------	-------------------	--------------------------	--------------------------	---------------------------

A total column will be presented for the disposition, demography, protocol deviation, medical history, prior/concomitant medication/procedure, and other subject information summaries.

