7.8.1. Primary and sensitivity analyses

The primary efficacy endpoints will be analyzed using the Full Analysis Set with confirmed fibrosis stage F2 or F3 and NAS ≥ 4 at baseline per independent review by a 3-pathologist panel. To evaluate the effect of BIO89-100 on liver histology, the proportions of subjects who met different histological responder criteria (defined in Section 4.1.1 and 4.1.2) at Week 24 will be summarized by treatment group based on central manual reads per central lab biopsy manual.

The Cochran-Mantel-Haenszel (CMH) test stratified by T2DM status (yes vs. no) and fibrosis stage (F2 vs. F3) will be used to compare the proportions of responders at Week 24 in each pegozafermin group versus placebo. The point estimates and 95% CI for the differences in proportions will be calculated. If two or more strata contain small cell counts (<5) that renders the stratified CMH test inappropriate, the primary analysis will use a logistic regression with treatment group indicator, stratification factors and baseline NAS score in the model.

The null hypotheses that there is no significant difference in proportion of subjects who met histological responder definition will be tested at significance level of 0.05 (two-sided) for each pegozafermin treatment group versus placebo. Type-1 error will not be adjusted for the multiplicity. Supportive analyses of each treatment QW arm vs. placebo QW arm and 44 mg Q2W arm vs. placebo Q2W arm will also be performed. The primary analysis will be repeated in all subjects with baseline and follow-up biopsies as a supportive analysis.

NAS grade of each component and NASH CRN fibrosis stage, along the shifts from baseline, will be summarized at Week 24 and different read source (central manual reads or PathAI machine reads). NAS total score and fibrosis score will be summarized descriptively at each protocol scheduled visit and different read source.

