7.12. Final Analysis

All safety and efficacy tables in final analysis will be presented as:-

Description	Placebo Only Pooled	Pegozafermin 15 mg QW	Pegozafermin 30 mg QW Only	Pegozafermin 44 mg Q2W	Placebo (main) and Pegozafermin 30 mg QW (Extension)
-------------	------------------------	--------------------------	----------------------------------	---------------------------	---

Groups “Placebo Only Pooled” and “Pegozafermin 30 mg QW Only” contain subjects who received the same treatment during the Main Study and the Extension Study. Group “Placebo (main) and Pegozafermin 30 mg QW (Extension)” contains subjects who switched to Pegozafermin 30 mg QW treatment in the Extension Study.

Safety summaries for final analysis will be presented by the actual treatment subject received based on the Safety Analysis Set except for subjects who re-randomized to Pegozafermin 30mg treatment group in the Extension Study. Subjects who switched the treatment group at Extension Study will be summarized under “Placebo (main) and Pegozafermin 30 mg QW (Extension)” group.

Final Efficacy analysis (secondary endpoints of Extension Study) will be performed based on the Full Analysis Set with confirmed fibrosis stage F2 or F3 and NAS ≥ 4 at baseline per 3- panel consensus read and by the randomized treatment group in Main Study.

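### The safety tables show one pooled placebo column that mixes 24 and 12 planned administrations, so injection-site reactions have no regimen-matched control

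*SAP*

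**What the plan says.** The general rule in SAP 7.1 is that "placebo QW and placebo Q2W will be pooled except for exposure summaries and pre-specified supportive analyses". The same section fixes the Main Study layout: "All applicable analyses for the primary analysis of the Main Study will be presented as" four columns, namely pooled placebo, 15 mg QW, 30 mg QW and 44 mg Q2W.

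SAP 7.12 does the same for the final analysis: "All safety and efficacy tables in final analysis will be presented as" five columns, again with a single pooled placebo-only column. The safety grouping rule in SAP 5.2 ignores regimen: "If a subject receives only placebo doses, then their actual treatment group will be placebo group".

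The dosing schedule differs by regimen. SAP 3.2 states: "IP will be administered over 24 weeks (includes 24 administrations in QW dose regimen and 12 administrations in Q2W dose regimen". The Extension repeats those counts.

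SAP 7.10.1 tabulates TEAEs as the proportion of subjects affected, by system organ class, preferred term and treatment group. It plans no rate per administration and no separate injection-site reaction table.

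The SAP has one regimen-matched comparison: "Supportive analyses of each treatment QW arm vs. placebo QW arm and 44 mg Q2W arm vs. placebo Q2W arm will also be performed". It stands in 7.8.1, under the primary efficacy endpoints.

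**The concern.** A subject given 24 administrations has twice as many occasions for a local reaction as a subject given 12. A table that counts subjects with at least one reaction therefore depends on the number of administrations as well as on the product given. The QW drug arms would be read against a control with fewer administrations than their own, and the 44 mg Q2W arm against a control with more.

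The two errors run in opposite directions. With no drug effect at all, the QW arms would tend to look worse than placebo and the Q2W arm better. The second matters more, because a real excess of local reactions on 44 mg Q2W could be hidden. The placebo mix also changes between the two analyses, because half of the placebo QW subjects move to drug at Week 24. The size of the error therefore shifts for a reason unrelated to tolerability.

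The documents do anticipate such reactions. Note u to the Schedule of Activities (Protocol 1.3) says: "The sites may take non-personally identifying photographs of potential injection site reactions (optional". The limited physical assessment in Protocol 8.2.1 includes looking at the injection sites.

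**Working it through.** The plan states no figure for this comparison, so there is none to reproduce. Its power figures concern histology and do not enter.

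**Inputs from the documents**
- Administrations: 24 (QW) and 12 (Q2W) in the Main Study, and the same again in the Extension, giving 48 and 24 (SAP 3.2). The Schedule of Activities agrees: Day 1 plus Weeks 1 to 23 is 24, and Day 1 plus alternate weeks from 2 to 22 is 12.
- Placebo subjects: 42 QW and 22 Q2W (SAP Table 1). After re-randomization 21 stay on placebo QW, so the final mix is about 21 to 22.

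**Mean planned administrations under pooled placebo**
- Main Study: (42×24 + 22×12)/64 = 1272/64 = 19.9. The QW drug arms have 24/19.9 = 1.21 times as many, and 44 mg Q2W has 12/19.9 = 0.60 times as many.
- Final analysis: (21×48 + 22×24)/43 = 1536/43 = 35.7. The ratios are 48/35.7 = 1.34 and 24/35.7 = 0.67.

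The earlier allocation (2:1:3:3:3, SAP 3.3) and the later one (16:8:6:24:15) both put placebo QW to Q2W at 2:1. The Main Study mix therefore does not depend on when subjects were randomized: (2×24 + 12)/3 = 20.

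**Effect on incidence**

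The documents give no reaction rate. Assume the same risk q per administration on drug and placebo, independent between administrations. The chance of at least one reaction in k administrations is 1 − (1 − q)^k. Pooled placebo is the weighted mean over its two parts. Since drug has no effect in this model, the whole difference between an active arm and pooled placebo is error.

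| q | QW | Q2W | Pooled placebo | QW minus pooled | Q2W minus pooled |
|---|---|---|---|---|---|
| Main, 0.25% | 5.8% | 3.0% | 4.8% | +1.0 | −1.9 |
| Main, 0.5% | 11.3% | 5.8% | 9.4% | +1.9 | −3.6 |
| Main, 1% | 21.4% | 11.4% | 18.0% | +3.5 | −6.6 |
| Final, 0.25% | 11.3% | 5.8% | 8.5% | +2.8 | −2.7 |
| Final, 0.5% | 21.4% | 11.3% | 16.2% | +5.1 | −4.9 |
| Final, 1% | 38.3% | 21.4% | 29.7% | +8.6 | −8.2 |

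Differences are in percentage points, taken before rounding. Example, Main Study at 1%: 1 − 0.99^24 = 0.2143 and 1 − 0.99^12 = 0.1136; pooled (42×0.2143 + 22×0.1136)/64 = 0.1797; differences +0.035 and −0.066.

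**With matched columns** the counts are 24 against 24 and 12 against 12 (48 against 48 and 24 against 24 by Week 48), and the expected difference under no drug effect is zero in both.

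**The case against.** Several points on the other side stand.

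- **Administrations are not injections.** The vial strength is redacted in Protocol 6.1, so injections per administration are unknown and could differ by dose. The figures above count planned administrations only, and early discontinuation would lower them.
- **The sizes are assumed.** If reactions cluster in susceptible subjects the errors shrink, towards zero if the same people react whatever the count. Protocol 2.3.1 lists the TEAEs seen in 5% or more of subjects in the earlier study, and no injection-site term is among them. Read as a 5% ceiling over 12 administrations, that gives q = 1 − 0.95^(1/12) = 0.43% and Main Study errors of about 1.6 (QW) and 3.1 points (Q2W). This reading is loose: some of those subjects were dosed Q2W, and reactions may be spread over several preferred terms.
- **Pooling buys precision.** Combine bias and sampling error in the Main Study control rate as √(bias² + variance), under the same model. For the QW arms pooled placebo does better than matched: 2.9 against 3.6 points at 0.25%, and 5.9 against 6.3 at 1%. For 44 mg Q2W pooled is better at 0.25% (3.3 against 3.6), about equal at 0.5% (5.1 against 5.0) and worse at 1% (8.1 against 6.8). This argues against replacing the pooled column, but not against adding to it.
- **Nothing is tested.** Safety analyses are descriptive, and injection-site reactions are neither a named safety endpoint (SAP 4.1.5) nor an event to monitor (Protocol 10.3.3). AEs are listed by subject, so a split could be made later, though a planned table is better than a post hoc one.
- **The matched analyses might extend to safety.** Protocol 9.4 mentions them in its general text, before the efficacy and safety subsections. But the SAP takes precedence (Protocol 9) and places them in 7.8.1. The amendment summary gives their purpose as robustness of the primary analysis, and SAP 7.10 and 7.12 contain no matched safety table. The table shells are separate documents and cannot be checked.

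**Conclusion.** The concern holds for events that accrue per administration, which in practice means injection-site reactions read from the TEAE incidence tables. The mismatch in planned administrations (19.9 against 24 and 12; 35.7 against 48 and 24) comes straight from the documents. If reactions accrue per administration, the direction does not depend on the rate: pooled placebo is too low a control for the QW arms and too high for 44 mg Q2W.

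The point sizes are illustrative. They rest on an assumed risk of 0.25% to 1%, equal across arms and independent between administrations, with every planned dose given.

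A reader might infer more than this, and the documents do not support it:
- **That the choice between 30 mg QW and 44 mg Q2W is biased.** Protocol 4.2 ties dose selection to efficacy data, in particular histology. The two active columns can also be compared directly without placebo.
- **That all adverse event comparisons are distorted.** Planned follow-up time is the same in both regimens, and nothing shows that TEAEs in general accrue per administration.
- **That a formal safety conclusion is at risk.** None is planned.

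No sample-size or power figure is affected. This is a modest point, worth making because the change is small.

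**What to change.** In SAP 7.10.1 and 7.12.1, keep the pooled placebo column and add descriptive placebo QW and placebo Q2W columns for injection-site reaction preferred terms. State that 15 mg and 30 mg QW are to be read against placebo QW, and 44 mg Q2W against placebo Q2W. Add these tables to the exceptions to the pooling rule in SAP 7.1. The overall TEAE summary can stay as it is.

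The cost is two columns in one table for each analysis. Regimen is already known to all parties (SAP 3.4), so showing it reveals nothing new. The drawback is small denominators: 42 and 22 in the Main Study, about 21 and 22 in the final analysis. The matched columns will be noisy and should be read beside the pooled one.

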7.2. Patient Disposition

Primary Analysis for Main Study

The number of patients screened and the number (percentage) of patients who failed screening (i.e., patients who consented to participate in the clinical study but were not subsequently randomized) and the reasons for screen failure will be summarized. The number of patients in each analysis set will be summarized by treatment group and overall.

In addition, the number of patients who discontinued the study IP and withdrew from the study will be summarized with treatment/study discontinuation reasons (including discontinuation due to COVID-19 pandemic).

The information including demography, screen failure reasons, eligibility criteria, end of treatment along with reasons, end of study along with reasons will be listed.

Final Analysis

In addition to repeat the disposition table of the Main Study following the final analysis layout, a separate summary table will be provided for subjects who switched the treatment in the Extension Study. The number (percentage) of patients who received at least one dose of pegozafermin in Extension Study, withdrew from the study, and discontinued the pegozafermin treatment along with the discontinuation reasons will be summarized.

The information including informed consent to Extension Study date, re-randomization, end of pegozafermin treatment dates, end of study dates, and discontinuation reasons will be listed.

